# Study Activities – Year 3 Open Label Extension

						Year 3 (	)pen Lab	Treatmen	t Period a					
	M 25	M 26	M 27	M 28	M 29	M 30	M 31	M 32	M 33	M 34	M 35	M 36	Unsch Visit	PD
Phone Visit b	X	X		X	X		X	X		X	X			
Pelvic Ultrasound @ : TVU, TAU												X		X c
Endometrial Biopsy d												X		X c
Pap Test														X c
Complete Physical Examination: including weight (W)												X (W)*		X (W)*
Gynecological (External Genitalia, Pelvic and Breast) Examination												X		X
Vital Signs			X			X			X			X	X	X
Mammogram e												X		X c
DXA Scan						X						X		X c
Clinical Safety Labs: Chemistry, Hematology, Lipid Panel and Urinalysis												X		X
Lipid Panel and Subset of Chemistry Labs: ALT, AST, Bilirubin and Alkaline Phosphatase			X			X			X					

	Year 3 Open Lab Treatment Period a													
	M 25	M 26	M 27	M 28	M 29	M 30	M 31	M 32	M 33	M 34	M 35	M 36	Unsch Visit	PD
Biomarker Sample: Serum Estradiol (E2) f						X						X		X
Pharmacokinetic Sample (PK): Elagolix and NETA Plasma Concentration f						X						X		X
Urine Pregnancy Test g,h	X	X	X	X	X	X	X	X	X	X	X	X		X
Contraception Counseling/Dispense Contraceptives as necessary i	X	X	X j	X	X	X j	X	X	X j	X	X	X j		X
Birth Control Attestation			X			X			X			X		X
UFS-QoL						X						X		X
C-SSRS – Since Last Visit			X			X			X			X		X
Interactive Response Technology (IRT)			X			X			X			X		X
Dispense Study Drug			X			X			X			X		
Drug Accountability b	X	X	X	X	X	X	X	X	X	X	X	X		X
Adverse Event Monitoring b	X	X	X	X	X	X	X	X	X	X	X	X	X	X
Concomitant Medication Review b	X	X	X	X	X	X	X	X	X	X	X	X	X	X

- @ Subjects with a finding of polyp on pelvic ultrasound during the Treatment Period will undergo evaluation per standard of care which may include an SIS.
- \* Complete physical examination; including weight (the subject should not wear shoes during weighing).
- a. Refer to Table 1 Visit and Assessment Windows, for allowable visit and assessment-specific windows during the Year 3 Treatment Period.
- b. Site staff to evaluate subjects compliance with taking study drug per protocol, assess ongoing adverse events, concomitant medications (if applicable), obtain the results of the subject's self-administered urine pregnancy test, and remind subjects of the importance of consistent use of appropriate and effective use of dual non-hormonal contraception.

- c. Premature Discontinuation prior to the time of the Treatment Month 30 does not require a Mammogram, DXA, Pelvic Ultrasound, or Pap test (i.e., received < 6 months of study drug during the Year 3 Treatment Period). Endometrial Biopsy is not required if the subject had an endometrial biopsy within the last 6 months. Refer to Section 5.3.1.1, Study Procedures, Endometrial Biopsy, and Bone Mineral Density (DXA scan) for additional details on performing DXA scan at Premature Discontinuation Visit.
- d. A negative urine pregnancy result should be obtained on the day of the endometrial biopsy, prior to performing the procedure. Endometrial Biopsy is not required if the subject had an endometrial biopsy within the last 6 months. Refer to Section 5.3.1.1, Study Procedures, Endometrial Biopsy for additional details.
- e. A Mammogram will be performed for all subjects who are 39 years of age or older at time of the scheduled study visit.
- f. Biomarker sample (E2), Pharmacokinetic (PK) (elagolix and NETA) samples can be drawn at any time during the visit.
- g. Study drug must not be dispensed if the subject has a positive urine pregnancy test result at a visit during the Treatment Period. A positive urine pregnancy test result must be confirmed with a quantitative serum pregnancy test. For any subject who has a positive serum pregnancy test result, a TVU must be performed during the first trimester of pregnancy to assess the gestational age and estimated date of delivery. The site will immediately inform the subject to discontinue study drug and the subject will be discontinued from the study at the point the pregnancy is confirmed.
- h. Home pregnancy test kits will be dispensed at on-site visits and will be self-administered at home by the subject and results will be reported to site.
- i. Subjects are required to continue the use of two forms of non-hormonal birth control throughout the Treatment Period. In addition, if the subject prematurely discontinues, the site should counsel the subject on the continued use of non-hormonal contraceptive use for at least 30 days after the last dose of study drug.
- j. Site should dispense enough contraceptives to carry subject over to the next on-site visit.

# Study Activities – Year 4 Open Label Extension

						Year 4 (	)pen Lab	Treatmen	t Period a					
	M 37	M 38	M 39	M 40	M 41	M 42	M 43	M 44	M 45	M 46	M 47	M 48	Unsch Visit	PD
Phone Visit b	X	X		X	X		X	X		X	X			
Pelvic Ultrasound @ : TVU, TAU												X		X c
Endometrial Biopsy d												X		X c
Pap Test												X		X c
Complete Physical Examination: including weight (W)												X (W)*		X (W)*
Gynecological (External Genitalia, Pelvic and Breast) Examination												X		X
Vital Signs			X			X			X			X	X	X
Mammogram e												X		X c
DXA Scan						X						X		X c
Clinical Safety Labs: Chemistry, Hematology, Lipid Panel and Urinalysis												X		X
Lipid Panel and Subset of Chemistry Labs: ALT, AST, Bilirubin and Alkaline Phosphatase			X			X			X					

						Year 4 (	Open Lab	Treatmen	t Period a					
	M 37	M 38	M 39	M 40	M 41	M 42	M 43	M 44	M 45	M 46	M 47	M 48	Unsch Visit	PD
Biomarker Sample: Serum Estradiol (E2) f						X						X		X
Pharmacokinetic Sample (PK): Elagolix and NETA Plasma Concentration f						X						X		X
Urine Pregnancy Test g,h	X	X	X	X	X	X	X	X	X	X	X	X		X
Contraception Counseling/Dispense Contraceptives as necessary	X	X	X j	X	X	X j	X	X	X j	X	X	X j		X
Birth Control Attestation			X			X			X			X		X
UFS-QoL						X						X		X
C-SSRS – Since Last Visit			X			X			X			X		X
Interactive Response Technology (IRT)			X			X			X			X		X
Dispense Study Drug			X			X			X					
Drug Accountability b	X	X	X	X	X	X	X	X	X	X	X	X		X
Adverse Event Monitoring b	X	X	X	X	X	X	X	X	X	X	X	X	X	X
Concomitant Medication Review b	X	X	X	X	X	X	X	X	X	X	X	X	X	X

- @ Subjects with a finding of polyp on pelvic ultrasound during the Treatment Period will undergo evaluation per standard of care which may include an SIS.
- \* Complete physical examination; including weight (the subject should not wear shoes during weighing).
- a. Refer to Table 1 Visit and Assessment Windows, for allowable visit and assessment-specific windows during the Year 4 Treatment Period.
- b. Site staff to evaluate subjects compliance with taking study drug per protocol, assess ongoing adverse events, concomitant medications (if applicable), obtain the results of the subject's self-administered urine pregnancy test, and remind subjects of the importance of consistent use of appropriate and effective use of dual non-hormonal contraception.

- c. Premature Discontinuation prior to the time of the Treatment Month 42 does not require a Mammogram, DXA, Pelvic Ultrasound, or Pap test (i.e., received < 6 months of study drug during the Year 4 Treatment Period). Endometrial Biopsy is not required if the subject had an endometrial biopsy within the last 6 months. Refer to Section 5.3.1.1, Study Procedures, Endometrial Biopsy, and Bone Mineral Density (DXA scan) for additional details on performing DXA scan at Premature Discontinuation Visit.
- d. A negative urine pregnancy result should be obtained on the day of the endometrial biopsy, prior to performing the procedure. Endometrial Biopsy is not required if the subject had an endometrial biopsy within the last 6 months. Refer to Section 5.3.1.1, Study Procedures.
- e. A Mammogram will be performed for all subjects who are 39 years of age or older at time of the scheduled study visit.
- f. Biomarker sample (E2), Pharmacokinetic (PK) (elagolix and NETA) samples can be drawn at any time during the visit.
- g. Study drug must not be dispensed if the subject has a positive urine pregnancy test result at a visit during the Treatment Period. A positive urine pregnancy test result must be confirmed with a quantitative serum pregnancy test. For any subject who has a positive serum pregnancy test result, a TVU must be performed during the first trimester of pregnancy to assess the gestational age and estimated date of delivery. The site will immediately inform the subject to discontinue study drug and the subject will be discontinued from the study at the point the pregnancy is confirmed.
- h. Home pregnancy test kits will be dispensed at on-site visits and will be self-administered at home by the subject and results will be reported to site.
- i. Subjects are required to continue the use of two forms of non-hormonal birth control throughout the Treatment Period. In addition, if the subject prematurely discontinues, the site should counsel the subject on the continued use of non-hormonal contraceptive use for at least 30 days after the last dose of study drug.
- j. Site should dispense enough contraceptives to carry subject over to the next on-site visit.

### Study Activities – Post-Treatment Follow-Up Period

	Pos	t-Treatment Follow-	U p a
	Month 1	Month 6	Month 12
On-site Visit	X		
Phone Visit		X	X
Physical Examination	X b		
Return to Menses Questionnaire c	X	X	
DXA Scan d		X	X
Pregnancy Test e	X (u, s)	$X^{f}(u)$	Xf (u)
Urine (u), serum (s)			
Serum Estradiol (E2) and FSH sample	X		
Lipid Panel and Subset of Chemistry Labs: ALT, AST, Bilirubin and Alkaline Phosphatase	X		
Review Adverse Events	$X^g$		
Review Adverse Events of Special Interest (Bone) h		X	X
Review Concomitant Medication	X	X	X

- a. Refer to Table 1 Visit and Assessment Windows, for allowable visit and assessment-specific windows during the Post-Treatment Follow-Up Period.
- b. Brief, symptom-directed examination to assess any ongoing AEs for resolution.
- c. If the subject has a documented menstrual period after the last dose of study drug, the subject may begin the use of hormonal contraception (e.g., oral or IUD) in place of non hormonal birth control.
- d. Site staff to contact subjects to ensure Month 6 and 12 DXA scans are scheduled within the visit window (refer to Table 1).
- e. A positive urine pregnancy test result must be confirmed with a serum pregnancy test. For any subject who has a positive serum pregnancy test result during the Post-Treatment Follow-Up Period, a TVU must be conducted as early as possible in the first trimester in order to assess the conception date. The subject will be discontinued from the Post-Treatment Follow-Up Period at the point the pregnancy is confirmed.
- f. A negative urine pregnancy test must be obtained within 2 days prior to performing the DXA. A positive urine pregnancy test result must be confirmed with a serum pregnancy test. For any subject who has a positive serum pregnancy test result, the DXA should not be performed. The subject will be discontinued from the Follow-Up Period at the point the pregnancy is confirmed.
- g. Any ongoing adverse events at the end of the Treatment Period will be reviewed for resolution during this visit.
- h. AESIs of bone fracture, clinically significant BMD loss, or newly diagnosed medically-related bone condition will be collected during the Post-Treatment Follow-Up Period.

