#### 5.2.1 Inclusion Criteria

- 1. Subject has voluntarily signed and dated the informed consent form (ICF), approved by an Institutional Review Board/Ethics Committee (IRB/EC), prior to any study-specific procedures including washout or screening procedures.
- 2. Subject is a premenopausal female 18 to 50 years of age at the time of Screening.
- 3. Subject has a diagnosis of uterine fibroids documented by a Pelvic Ultrasound (TAU, TVU) assessed by a central reader and verification that a uterine fibroid meets at least one of the following criteria:
  - Intramural, submucosal non-pedunculated fibroid with a diameter ≥ 2 cm (longest diameter)
  - Subserosal fibroid  $\geq 4$  cm (longest diameter)
  - Multiple fibroids with a total uterine volume of  $\geq 200 \text{ cm}^3$  to  $\leq 2,500 \text{ cm}^3$
- Subject has HMB associated with uterine fibroids as evidenced by MBL > 80 mL during each of two menses in Screening as measured by the alkaline hematin method.
- 5. Subject has a Screening FSH level of < 35 mIU/mL (35 IU/L).

- 6. Subject must have a negative urine and/or serum pregnancy test(s) during the Washout (if applicable) and/or Screening Periods, and a negative urine pregnancy test just prior to administration of the first dose of study drug.
- 7. Subject must agree to use two forms of non-hormonal contraception (dual contraception) consistently during the Washout (if applicable), Screening, Treatment Periods and through the end of Month 1 of the Post-Treatment Follow-Up Period. Acceptable methods of dual contraception include the following combinations:
  - Condom with spermicide (foam, gel or polymer film)
  - Diaphragm with spermicide (condom may or may not be used)
  - Cervical cap with spermicide (condom may or may not be used) Subject is not required to use dual contraception methods if:
  - Sexual partner(s) is vasectomized, at least 6 months prior to Screening.
  - Subject practices total abstinence from sexual intercourse, as the preferred lifestyle of the subject; periodic abstinence is not acceptable and requires dual non-hormonal contraception.
  - Subject had a bilateral tubal ligation or bilateral tubal occlusion, at least 4 months prior to Screening.
  - Subject is not sexually active with men; however, periodic sexual relationship(s) with men require the use of study defined dual non-hormonal contraception.

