## 5.2.3.5 Prohibited Therapy

All hormonal forms of birth control (except the emergency contraceptive pill, levonorgestrel 1.5 mg [such as Plan B®], or ulipristal acetate 30 mg [such as Ella® or EllaOne®]) are prohibited during the Washout, Screening, Treatment Periods and until the Post-Treatment Follow-Up Period Month 1. Subjects may start hormonal contraception after completion of Post-Treatment Follow-Up Period Month 1, and having a negative urine pregnancy test after 1 month off of study drug and returned to menses. If the Subject has not returned to menses by Month 1 in the Post-Treatment Follow-Up Period, the Investigator would use acceptable medical practice to reinitiate hormonal contraceptive (e.g., pregnancy test, FSH, induction of withdrawal bleed, etc.).

For subjects who are prescribed/administered the emergency contraceptive pill during the study, the information should be captured in the source documents and eCRF and the AbbVie TA MD must be informed.

Tranexamic acid should not be taken during the Screening and Treatment Periods, however tranexamic acid, if necessary, can be prescribed following completion of the Treatment Period and the subject has returned to first full menses. Should the subject be prescribed tranexamic acid during the Treatment Period, they will be discontinued and will enter the Post-Treatment Follow-Up Period.

Any supplements or herbal remedies used to treat premenstrual or gynecological problems, such as black cohosh, are excluded.

The following medications should not be taken during the Washout (if applicable), Screening, and the Treatment Periods.

[figure not shown]
[figure not shown]

Table 3. Prohibited Medications

GnRH agonist	Leuprolide acetate (Lupron®)	
Prohibited During the Washout, Screening and Treatment Periods and Through Follow-Up Month 1		
Hormonal and Non-hormonal Estrogen Supplements, ** such as:	GnRH agonists: nafarelin acetate (Synarel®), goserlin acetate (Zoladex®)	
	GnRH antagonists (other than study elagolix)	
	Danazol (Danocrine®, Cyclomen®)	
	Medroxyprogesterone acetate (Depo-Provera®, Provera®)	
	Oral contraceptives	
	Estrogen preparations*	
	Testosterone preparations	
	Other progestins* (oral, vaginal, transdermal, implantable, IUD, or LNG-IUS, except emergency contraception)	
	HCG or HCG products	
	Glucocorticoids, oral or injectable (chronic use only)	
	Other progestins (oral, vaginal, IUDs, implantable)	
	Levonorgestrel (except emergency contraception, i.e., levonorgestrel 1.5 mg)	

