## Table 3. Prohibited Medications (Continued)

Prohibited During the Washout, Screening, and Treatment Periods		
Moderate or strong CYP3A Inducers, 	Strong Inducers:	
and Anti-epileptic medications, such	St. John's Wort	
as:	Rifampin	
	Carbamazepine	
	Phenytoin	
	Dexamethasone chronic use	
	Moderate Inducers:	
	Bosentan	
	Efavirenz	
	Etravirine	
	Modafinil	
	Nafcillin	
Strong organic anion transporting	Cyclosporine	
polypeptide 1B1 (OATP1B1) inhibitors such as:	Rifampin (single dose)	
	eatment, and Post-Treatment Follow-Up Periods	
Osteoporosis Medications Bisphosphonates, RANKL, [Receptor activator of nuclear factor-κ B ligand] inhibitors, Anabolic Bone Agents or rPTH, such as:	Denosumab, Teriparatide Fosamax ® , Fosamax Plus D ® , Binosto ® , Boniva ® , Reclast ® , Zometa ® , Prolia ® , XGEVA ® , Forteo ® , Actonel ® , Atelvia ® , Miacalcin ® , Fortical ®	
Synthetic Prostaglandin E1 (PGE1)	Misoprostol (Cytotec®, Arthrotec®)	
Analogs, such as:	Single use of PGE1 for cervical preparation prior to biopsy is allowed; chronic use is prohibited	
Glucocorticoids/Corticosteroids, systemic administration (oral, IM or IV)	Except for short-term use as noted in this protocol.	
Oral Retinoids (topical applications are permitted), Teratogens such as:	Topiramate, Accutane® (isotretinoin) and other oral retinoids	

- \* E2/NETA will be taken by subjects randomized to the E2/NETA dose group.
- # Due to the extensive list of herbal remedies and supplements, please contact the AbbVie TA MD for any that may be prohibited.
- % Subjects may begin the use of hormonal contraceptives following completion of the Treatment Period and must have a negative urine pregnancy test 1 month off of study drug and return to menses. Tranexamic acid, if necessary can be prescribed following completion of the Treatment Period and the subject has returned to first full menses.

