## 5.2.4 Contraception Recommendations

### **Contraception Counseling/Dispensing Contraceptives**

Investigators and study staff will be trained by the Sponsor on the importance of contraception in this clinical trial. Subjects (excluding those subjects who have had a bilateral tubal ligation or bilateral tubal occlusion) will be counseled by the Investigator or designated study staff at every visit throughout study participation on the importance of pregnancy prevention and the use of appropriate and effective methods of contraception.

Subjects must agree to use two forms of non-hormonal contraception (dual contraception) consistently throughout the Washout (if applicable), Screening and Treatment Periods and the first month of the Post-Treatment Follow-Up Period. Subjects may begin the use of hormonal contraception (e.g., oral or IUD) after completion of the Post-Treatment Follow-Up Month 1 visit and has a negative urine pregnancy test after 1 month off study drug and return to menses.

Acceptable methods of dual non-hormonal contraception include the following combinations:

- Condom with spermicide (foam, gel or polymer film)
- Diaphragm with spermicide (condom may or may not be used)
- Cervical cap with spermicide (condom may or may not be used)

Subjects are not required to use dual contraception methods if:

- Sexual partner(s) is vasectomized at least 6 months prior to screening
- Subject practices total abstinence from sexual intercourse, as the preferred lifestyle of the subject; periodic abstinence is not acceptable
- Subject had a bilateral tubal ligation or bilateral tubal occlusion at least 4 months prior to screening.
- Subject is not sexually active with men; however, periodic sexual relationship(s) with men requires the use of dual non-hormonal contraception as indicated above.
- Subject has begun the use of hormonal contraception after the Post-Treatment Follow-Up Month 1 visit.
- Subjects may begin the use of hormonal contraception after the Post-Treatment Follow-Up Month 1 visit, provided she has a negative urine pregnancy test 1 month off of study drug and has returned to menses. If the Subject has not returned to menses by Month 1, the Investigator would use acceptable medical practice to reinitiate hormonal contraceptive (e.g., pregnancy test, FSH, induction of withdrawal bleed).

The following measures will be taken to help ensure pregnancy prevention during the study.

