## 5.3.1.1 Study Procedures

[figure not shown]
The study procedures outlined in Appendix C are discussed in detail in this section, with the exception of monitoring study drug accountability (Section 5.5.7), contraception counseling/contraceptive dispensing (Section 5.2.4), the collection of concomitant medication (Section 5.2.3) and adverse event information (Section 6.0). All study data will be recorded on the eCRFs with the exception of the select ePRO data and data from the central lab/imaging vendor.

The Screening Period will occur within approximately 2.5 to 5 months prior to administration of the first dose of study drug on Day 1 (Randomization). For procedures performed during the Screening Period and subsequently repeated (as allowed per protocol or at the discretion of the AbbVie TA SD), the procedure performed closest to dosing will serve as a baseline for clinical assessment.

Study procedures during the Treatment and Post-Treatment Follow-Up Periods should be performed within the visit windows specified in Table 1. Scheduled monthly visits during the Treatment and Post-Treatment Follow-Up Periods are based on a 28-day month.

This protocol provides recommendations regarding the sequence of procedures to be performed during the study. In no case should these recommendations outweigh clinical judgment or standard of care. If the protocol indicates that the AbbVie TA SD or MD is to be contacted prior to performing a procedure, yet the timing of the request would either interrupt a procedure or would interfere with standard of care and clinical judgment, then clinical judgment should prevail and the AbbVie TA MD should be notified afterwards.

Due to the long Screening Period, eligibility should be assessed throughout the Screening Period, including just prior to randomization to ensure that the subject continues to meet eligibility and that the results from all screening procedures are available prior to randomization.

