#### Return to Menses

Subjects will be asked about return to menses using the Return to Menses Questionnaire in the Post-Treatment Follow-Up Period, as outlined in the Study Activities, Appendix C. Site staff will ask subjects if they have had a menstrual period since discontinuation of study drug and record subjects' responses on the site tablet. If the subject indicates she has not returned to full menses, site staff will continue assess menstruation and repeat the questionnaire at subsequent post-treatment follow-up visits, as applicable. The date when full menses returned will be documented in the source documents and eCRFs.

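### Appendix C follow-up footnote c lets hormonal contraception start on a menstrual period alone, contrary to Sections 5.2.3.5 and 5.2.4, Table 3 and inclusion criterion 7 (wrong as written, minor)

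*Protocol*

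**What the plan says.** **Appendix C, post-treatment follow-up table, footnote c.** The note is attached to the Return to Menses Questionnaire and reads: "If the subject has a documented menstrual period after the last dose of study drug, the subject may begin the use of hormonal contraception". It goes on to say that this replaces non-hormonal birth control. It names no visit, no minimum time off drug and no pregnancy test, and it does not refer to another section.

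**Section 5.2.3.5, text.** Hormonal contraception may start "after completion of Post-Treatment Follow-Up Period Month 1, and having a negative urine pregnancy test after 1 month off of study drug", and once menses has returned.

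**Section 5.2.4.** The same rule: "after completion of the Post-Treatment Follow-Up Month 1 visit and has a negative urine pregnancy test after 1 month off study drug", again with return to menses.

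**Table 3.** Oral contraceptives and progestins, including intrauterine forms, stand under the heading "Prohibited During the Washout, Screening and Treatment Periods and Through Follow-Up Month 1". The footnote marked % adds that women "must have a negative urine pregnancy test 1 month off of study drug and return to menses".

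**Inclusion criterion 7 (Section 5.2.1).** Dual non-hormonal contraception is required "through the end of Month 1 of the Post-Treatment Follow-Up Period".

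**Appendix C, treatment tables.** Footnote q (Year 1) and footnote i (Years 2, 3 and 4) tell sites to counsel women who discontinue early to keep to non-hormonal methods for at least 30 days after the last dose.

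**Return to Menses (Section 5.3.1.1).** During follow-up, site staff "ask subjects if they have had a menstrual period since discontinuation of study drug". The follow-up table schedules this first at Month 1.

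**The concern.** One question, when a woman may switch to hormonal contraception after stopping study drug, gets two answers in the same protocol. A woman who bleeds before the end of follow-up Month 1 may switch under footnote c. She may not under Section 5.2.3.5, Section 5.2.4, Table 3 or criterion 7. The looser rule sits in the schedule of activities, which sites work from during follow-up.

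What is at stake is a pregnancy safeguard. Section 3.2.3 says that elagolix does not block ovulation, that pregnancies have occurred on treatment, and that two pregnancies with congenital malformations were seen in earlier Phase 2 studies. Section 5.2.4 has sites tell women that study drug may change bleeding patterns. For these reasons the body of the protocol pairs the return of bleeding with a negative test and a month off drug. Footnote c keeps only the bleeding.

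**Working it through.** This is a comparison of texts. The only arithmetic is the timing of one visit.

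**Step 1. Conditions side by side**

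| Place | Month 1 completed, or other minimum time | Negative urine test after 1 month off drug | Menses |
|---|---|---|---|
| Appendix C follow-up, footnote c | not stated | not stated | required |
| Section 5.2.3.5, text | Month 1 completed | required | required, may be relaxed |
| Section 5.2.4 | Month 1 visit completed | required | required, may be relaxed |
| Table 3, heading | barred through Month 1 | not stated | not stated |
| Table 3, footnote % | 1 month, through the timing of the test | required | required |
| Inclusion criterion 7 | non-hormonal methods to end of Month 1 | not stated | not stated |
| Appendix C footnotes q and i (early discontinuers only) | 30 days after last dose | not stated | not stated |

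Of the three permission rules in Section 5.2.3.5, Section 5.2.4 and footnote c, only footnote c omits both the time condition and the test.

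**Step 2. Does the exception close the gap?** Sections 5.2.3.5 and 5.2.4 let the investigator use accepted medical practice to restart hormonal contraception if menses has not returned by Month 1. That relaxes the menses condition. Footnote c keeps menses and drops the other two, so the exception does not reconcile the texts.

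**Step 3. Does the visit schedule close the gap?** Inputs:
- A month is 28 days (Section 1.3, Definition of Terms; repeated in Section 5.3.1.1).
- The follow-up visit window is 7 days either way (Table 1).
- The month is taken to run from the last dose, since Section 5.1 dates the follow-up period from it.

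Results:
- Earliest in-window Month 1 visit: 28 − 7 = day 21.
- Latest in-window Month 1 visit: 28 + 7 = day 35.
- A test on day 21 is 28 − 21 = 7 days short of a 28-day month, and 30 − 21 = 9 days short of the 30 days in footnotes q and i.
- A visit exactly on day 28 is 30 − 28 = 2 days short of those 30 days.

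So a woman seen on day 21 who reports a period satisfies footnote c that day. She has a test result from the visit, but not one taken after a month off drug.

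**Step 4. Is bleeding by then plausible?** Section 3.2.2 reports that, among elagolix-treated women in Phase 2b who were amenorrheic on entering follow-up, 52% (Cohort 1) and 59% (Cohort 2) had returned to menses at Month 1. Those figures do not show how many bled before day 21 or day 28. They show only that menses by about the time of this visit is common.

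**The case against.** The strongest reply is that the schedule applies the missing conditions in practice. Footnote c hangs on a questionnaire first given at the on-site Month 1 visit. Urine and serum pregnancy tests are in the same column, and footnote e removes a woman with a confirmed pregnancy from follow-up. No earlier follow-up visit is scheduled. The protocol also describes Appendix C as a summary, and Section 5.3.1.1 sends readers to Section 5.2.4 for contraception counseling. On this view footnote c is shorthand for Section 5.2.4.

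Most of this stands, and it is why the effect is small. A site that records menses at an on-time Month 1 visit and acts on the test result will come close to the full rule. It does not remove the error, for three reasons. Footnote c does not confine the record of menses to that visit. It does not make the permission depend on the test result. And the window lets the visit fall before a month off drug has passed. No text says that the body overrides the appendix.

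A reader might infer that the schedule sets no minimum time off drug for anyone. The documents do not support that: footnotes q and i give 30 days to women who discontinue early. A reader might also see the footnote's mention of oral and intrauterine methods as a separate contradiction of Table 3. It is not, because Section 5.2.4 uses the same examples for the period after Month 1.

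**Conclusion.** Footnote c is wrong as written, and the matter is minor. It omits two conditions that Sections 5.2.3.5 and 5.2.4 both state, it permits a start that Table 3 and criterion 7 rule out before the end of Month 1, and for early discontinuers it omits the 30-day period in footnotes q and i.

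In time, the gap at an in-window visit is at most 7 days against a 28-day month, or 9 days against 30 days, assuming that the month runs from the last dose. It could be longer if menses is documented before the Month 1 visit, which footnote c does not exclude. No count of women can be given, because the documents report no uptake of hormonal contraception after treatment.

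Two larger conclusions might be drawn and should not be. One is that women would switch without any pregnancy test; tests are scheduled at Month 1, and the fault is that the permission is not tied to their result. The other is that contraception counseling stops in follow-up because that table has no row for it; Section 5.2.4 requires counseling at every visit, except for women with tubal ligation or occlusion. No SAP analysis uses the condition in footnote c, so no estimate, test or sample size changes.

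**What to change.** Reword footnote c along these lines: *Hormonal contraception may begin only once the follow-up Month 1 visit is complete, a urine pregnancy test taken after 1 month off study drug is negative, and menses has returned (see Sections 5.2.3.5 and 5.2.4, including the allowance for women without menses by Month 1).*

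The cost is one sentence in one footnote. Visits, windows, scheduled tests, data fields and the SAP stay as they are. A woman whose Month 1 visit falls before a full month off drug would need a later negative urine test before switching. Sections 5.2.3.5 and 5.2.4 already require that, so the rewording adds no new burden.
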